## 12.5 Glossary of Abbreviations

Term/Abbreviation	Definition
ANCOVA	analysis of covariance
ANOVA	analysis of variance
AUC	area under the curve
BOTOX®	Botulinum Toxin Type A Purified Neurotoxin Complex (US adopted name onabotulinumtoxinA), referred to as BOTOX
BUN	blood urea nitrogen
CFR	Code of Federal Regulations
CI	confidence interval
CIC	clean intermittent catheterization
CMH	Cochran-Mantel-Haenszel
CNS	central nervous system
DLPP	detrusor leak point pressure
DRC	Data Review Committee
EBC	expected bladder capacity
eCRF	electronic case report form
EDC	electronic data capture
eGFR	estimated glomerular filtration rate
ELISA	enzyme linked immunosorbent assay
EU	European Union
FDA	Food and Drug Administration
GCP	Good Clinical Practice
HEENT	head, eyes, ears, nose, throat
HIPAA	Health Insurance Portability and Accountability Act
HRQOL	health-related quality of life
ICH	International Conference on Harmonisation
IDC	involuntary detrusor contraction
IDR	independent drug reconstitutor
IEC	Independent Ethics Committee
IRB	Institutional Review Board
IV	intravenous
IVRS	interactive voice response system
IWRS	interactive web response system

LS	least squares
MCC	maximum cystometric capacity
mITT	modified intent-to-treat
NDO	neurogenic detrusor overactivity
OAB	overactive bladder
Pdet Max1stIDC	maximum detrusor pressure during the first IDC
Pdet Max	maximum detrusor pressure during the storage phase
PinQ	Pediatric Incontinence Questionnaire
PP	per protocol
RBC	red blood cell
SD	standard deviation
SNAP-25	synaptosomal protein of molecular weight 25 kDa
SNARE	soluble NSF [N-ethylmaleimide-sensitive factor] attachment protein receptor
T1	thoracic vertebra level 1
TBS	Treatment Benefit Scale
TRPV1	transient receptor potential vanilloid 1
UDS	urodynamic studies
US	United States (of America)
UTI	urinary tract infection
WBC	white blood cell

## 12.6 Protocol Amendment 1 Summary

Title: BOTOX® in the Treatment of Urinary Incontinence Due to Neurogenic Detrusor Overactivity in Patients 8 to 17 Years of Age

Protocol 191622-120 Amendment 1

Date of Amendment: October 2013

### Amendment Summary

This summary includes changes made to Protocol 191622-120 (14 January 2013).

Following is a summary of content-oriented changes that were made to each section of the protocol, and a brief rationale for these changes. Minor editorial and document formatting revisions have not been summarized.

Section	Revision	Rationale
Protocol Title Page	Removed emergency contact number	This information is now included in a study specific contacts page.
Investigator signature page	Removed Study Location Added text indicating that the Investigator will ensure all participating personnel are adequately informed about the protocol Removed provision for multiple investigator signatures	Global change to Allergan's protocol template

[REDACTED]

[REDACTED]

[REDACTED]

[REDACTED]

Section	Revision	Rationale
[REDACTED]	[REDACTED]	[REDACTED]
[REDACTED]	[REDACTED]	[REDACTED]
[REDACTED]	[REDACTED]	[REDACTED]
Clarified that indwelling catheters are permitted overnight if needed, but that indwelling catheterization is not permitted during diary collection periods	The use of an indwelling catheter overnight is common practice in the patient population intended to be recruited to this study; therefore their use is allowed. However, since the first morning catheterization urine volume is an efficacy parameter, as well as presence or absence of night time incontinence, indwelling catheters will not be allowed during diary collection periods.	[REDACTED]
[REDACTED]	[REDACTED]	[REDACTED]
[REDACTED]	[REDACTED]	[REDACTED]
Study Schedule (Table 1)/6.3.8 Bladder and Kidney Ultrasound	Added requirement to measure bladder wall thickness by ultrasound at the screening visit	Patients may have urinary bladder fibrosis which is linked with poor compliance. Measurement of bladder wall thickness will allow for further characterization of the patient population being studied.

Section	Revision	Rationale
4.5.1.1 Definition of Females of Childbearing Potential and Acceptable Contraceptive Methods	Removed text relating to females becoming sexually active when postmenarche	Females who are postmenarche are considered to be of childbearing potential in a biological context; therefore text removed
5.9.4 Treatment Procedure	Added text to clarify that patients should remain under observation at the clinic for longer than 30 minutes if local site practice requires this	The protocol provides a minimum time period for observation after treatment; however, local site practice should take precedence if it requires a longer observation period.
6.3.2 Medical History	Clarified what relevant medical history should be collected and added a sentence to include the collection of the presence or absence of selected baseline characteristics	This provides guidance for sites, and the collection of baseline characteristics will allow further characterization of the patient population being studied.
6.3.4 Weight and Height	Amended text to clarify when height and weight should be measured	Clarifications provided to ensure that data are available when needed for certain calculations, eg, dose based on patient weight, estimate of glomerular filtration rate
6.3.8 Bladder and Kidney Ultrasound	Amended text to clarify when ultrasound is to be performed	Clarification
6.3.11 Renal Function Testing	New section	Renal function assessment (estimated glomerular filtration rate based on serum creatinine levels and patient height) was added based on Regulatory Agency feedback.
7.4 Safety Analysis	Addition of renal function assessment	Renal function, as assessed by estimated glomerular filtration rate, is now a safety parameter.
8.7 Early Discontinuation of Patients	Clarification added in relation to follow up in patients who agree to follow-up after exiting the study early	Clarification regarding time period of follow-up included based on Regulatory Agency feedback
9.1.1 Adverse Event	Additional text regarding the documentation of disease progression/lack of efficacy	Global change to Allergan's protocol template
10.3.1 Patient Privacy and 10.4.2 Case Report Form Completion	Amended wording	To reflect global change to Allergan's protocol template

Section	Revision	Rationale
12.1.1 BOTOX 50 U	Amended lower body weight range from 15 kg (33 lbs) to 14 kg (31 lbs)	Typographical error in original protocol
12.1.2 BOTOX 100 U		
12.1.3 BOTOX 200 U		
12.3.3 Site Urodynamic Qualification	Added clarification that the sample urodynamic tracing can be from a urodynamic assessment of a pediatric patient who is comparable in age to the age group of study participants and that traces will be anonymized	To clarify sample tracing procedures and comply with patient privacy laws
12.3.5 Urodynamic Annotation	Added that first leakage can occur with or without an IDC and annotations should be reflected accordingly	Clarification
12.3.8 Parameters to be recorded on the worksheet	Added volume at first IDC	Additional measurement required for calculation worksheet
12.5 Package Insert	Removed section	Global change to Allergan's protocol template

## 12.7 Protocol Amendment 2 Summary

Title: BOTOX® in the Treatment of Urinary Incontinence Due to Neurogenic Detrusor Overactivity in Patients 5 to 17 Years of Age

Protocol 191622-120 Amendment 2

Date of Amendment: April 2016

### Amendment Summary

This summary includes changes made to Protocol 191622-120 (4 October 2013).

Following is a summary of content-oriented changes that were made to each section of the protocol, and a brief rationale for these changes. Minor editorial and document formatting revisions have not been summarized.

Section	Revision	Rationale
Title and Study Population [REDACTED]	Changed minimum age to 5 [REDACTED]	Updated patient inclusion criterion [REDACTED]
Inclusion criteria	Reduced minimum age requirement from 8 years old to 5 years old	Expand age range for inclusion in the study.
Section 5.9.1	Day of Treatment Criteria: added “or presence of significant leukocyturia (e.g. $\geq$ 30 WBC/HPF)” to the criteria which the investigator should consider when determining if the patient has a UTI	To ensure patient safety, added that in addition to considering patient symptoms, urine culture results and the need for antibiotic treatment, the investigator should also consider the presence of clinically significant leukocyturia when determining if the patient has a UTI. Also provided an example of clinically significant leukocyturia as $\geq$ 30 WBC/HPF.
Section 5.9.3	Use of Anesthesia: added “which could include conscious sedation”	For clarity
Section 12.1	Updated dosing table to add row for lower body weight	To include dosing information for a younger patient population.

## 12.8 Protocol Amendment 3 Summary

Title: BOTOX® in the Treatment of Urinary Incontinence Due to Neurogenic Detrusor Overactivity in Patients 5 to 17 Years of Age

Protocol 191622-120 Amendment 3

Date of Amendment: September 2017

### Amendment Summary

Following is a summary of content-oriented changes that were made to each section of the protocol, and a brief rationale for these changes. Minor editorial and document formatting revisions have not been summarized.

Sections	Revision	Rationale
Synopsis Section 4.4: Number of Patients Section 7.7: Sample Size Calculation	Decreased the sample size from N=132 to N=102	Due to enrollment challenges, the sample size was recalculated. While the revised sample size will provide a wider confidence interval than the current sample size, the proposed reduction should not negatively affect the clinical and scientific integrity of the study. The FDA has concurred with this plan.
Section 7.1: Analysis Populations	Deleted Per-protocol population	To reflect current company standard for not performing analyses on per-protocol population for superiority trials.

Table 3	Initial Imputed Date Algorithm.....	11
Table 4	Clinical Laboratory PCS Criteria.....	30
Table 5	Vital Sign PCS Criteria	32

1. Introduction

This document details the planned analysis for Study 191622-120. This study is a multicenter, randomized, double-blind, parallel group study to evaluate the safety and efficacy of BOTOX for the treatment of urinary incontinence due to neurogenic detrusor overactivity (NDO) in patients 5 to 17 years of age who have not been adequately managed with anticholinergic therapy.

There will only be one analysis for this study. When all patients in Study 191622-120 exit the study there will a database lock (DBL) and a clinical study report (CSR) will be generated. This analysis plan outlines the outputs to be included in the CSR.

1.1 Primary Study Objectives and Design

The primary objective of this study is to evaluate the safety and efficacy of BOTOX for the treatment of urinary incontinence due to NDO in patients 5 to 17 years of age who have not been adequately managed with anticholinergic therapy. Patients in this study are randomized to 1 of 3 treatment groups in a 1:1:1 ratio:

- 50 units (U) BOTOX (not to exceed 6 U/kg)
- 100 U BOTOX (not to exceed 6 U/kg)
- 200 U BOTOX (not to exceed 6 U/kg)

In order to ensure that the upper dosing limit of 6 U/kg is not exceeded, the actual dose administered is adjusted based on patient weight, if necessary.

Patients will be evaluated during a screening period for eligibility. Eligible patients will be randomized and receive treatment/injection on Day 1. Patients are centrally randomized. In order to ensure balance across treatment groups, patients are stratified by age (< 12 years or \geq 12 years), and baseline daytime urinary incontinence episodes (a total of \leq 6 episodes or $>$ 6 episodes over the 2-day diary collection period).

Patients will participate in the study until one of the following exit criteria is met, whichever occurs first:

- patient has qualified for retreatment (retreatment to occur in the extension study 191622-121, for patients who elect and qualify to enroll),
- patient has completed 48 weeks after treatment (BOTOX injection), if qualification for retreatment does not occur (i.e., completes the 48 week visit), or
- patient prematurely discontinues the study

In this study, patients are evaluated at scheduled visits at 2, 6, and 12 weeks after treatment/injection (week 2, 6 and 12 visits). After the week 12 visit, there are alternating telephone and clinic visits every 6 weeks until the patient exits the study. Patients will exit the study once they qualify for retreatment. The visit where the patient qualifies for retreatment will also become the exit visit. Alternatively, if qualification for retreatment does not occur, patients will exit the study 48 weeks after study drug injection.

The primary efficacy measure is daytime urinary incontinence episodes, and the primary time point is week 6.

1.2 Secondary and Other Objectives

Not applicable.

1.3 Sample Size

The sample size calculation for this study is determined empirically. Sample size assessment is presented in Section 7.7 of the study protocol.

1.4 Experimental Unit and Analysis Unit

The experimental unit is study subject. The primary efficacy assessment is daytime urinary incontinence episode measured at the patient level.

2. Analysis Populations and Data Conventions

2.1 Analysis Populations

Patients in this study are randomized to one of three treatment groups, namely, 50, 100 or 200 U BOTOX treatment groups. Within each randomization group, the dose that is actually received by a patient can vary due to the dose limit of 6 U/kg (i.e., the dose is adjusted based on the patient's weight). [Table 1](#) presents the BOTOX treatment arms to be used for analysis, if different than randomized.

Table 1 BOTOX Treatment Groups Based on Actual Dose Administered

Actual Dose Administered	BOTOX Treatment Group
< 75 U	50 U BOTOX
75 U \geq and < 150 U	100 U BOTOX
\geq 150 U	200 U BOTOX

In order to maintain blinding of the BOTOX dose received, the drug is reconstituted by an independent drug reconstitutor (IDR) based on randomization assigned by IVRS/IWRS (which also includes the patient's weight as provided in IVRS/IWRS). Study drug accountability and reconstitution records are then reviewed and confirmed by independent drug monitors (IDM). If an incorrect dose was administered, the IDM will complete the "Incorrect Unit Dose Administered" form and the "incorrect unit dose administered" will be entered into the electronic case report form (eCRF).

Patients will be assigned to actual treatment groups for analysis purposes as follows:

1. If the "incorrect unit dose administered" is populated in the eCRF, this dose will be used and adjusted per [Table 1](#) above.
2. If the "incorrect unit dose administered" is not populated in the eCRF, then the randomized dose (ie, 50U, 100U, or 200U) and the patient's weight recorded in IVRS/IWRS at the time of randomization will be utilized to determine the actual dose administered as described in section 12.1 of the study protocol. The dose administered will then be adjusted per [Table 1](#) above.

Two populations will be used in the statistical analysis of this study: modified intent-to-treat (mITT) and safety.

The analysis of demographics, baseline characteristics and efficacy will be based on the mITT population while the safety population will be used for all safety analysis.

Modified Intent-to-Treat (mITT) Population

The mITT population will include all randomized patients who received BOTOX injection on Day 1 (randomization day and date of injection). Patients in the mITT population will be analyzed on an as-randomized basis, except for patients who received less than their randomized dose due to the patient's weight and the dose limit of 6 U/kg (as per the protocol). Such patients will be grouped to the nearest dose group based on the dose they actually received. Thus, patients that receive a dose of < 75 U will be assigned to the 50 U treatment group, patients that received a dose in the range of ≥ 75 U and < 150 will be assigned to the 100 U treatment group, while patients that received ≥ 150 U will be assigned to the 200 U group ([Table 1](#)). Patients who received a different dose for any other reason than the 6 U/kg cap, will be analyzed according to the dose they were randomized to.

Safety Population

The safety population will include all patients who underwent the treatment procedure and received study drug on randomization/day 1. Safety analyses will be based on actual treatment received. Patients who received a different dose than the dose they were randomized to (as a result of either the 6 U/kg weight cap or any other reason) will be grouped according to the nearest dose group based on the actual dose received, as presented in [Table 1](#).

2.3 Data Conventions

The following data conventions will be applied to all analyses.

- A patient's weight adjusted dose will be derived using the randomization information and the patient's actual weight provided in IVRS/IWRS at baseline.
- Unless stated otherwise, all statistical tests will be at a 2-sided significance level of 0.05. P-values ≤ 0.050 will be considered statistically significant.
- Since the qualification for retreatment may occur anytime from week 12 onwards, no statistical tests for pairwise comparison of treatment groups will be performed for any visit beyond week 12.
- The type III sums of squares will be used for all analysis of covariance models (ANCOVA).
- The variance for Kaplan-Meier estimates will be calculated using Greenwood's formula.
- Descriptive statistics for continuous variables include the sample size (N), mean, SD, median, minimum (min), first quartile (Q1), third quartile (Q3), and maximum (max).

- Summary statistics for categorical variables include the sample size (N), frequency count and percent.
- The Medical Dictionary for Regulatory Activities (MedDRA) dictionary will be used to code all adverse events (AEs) and medical history.
- World Health Organization Drug Dictionary Enhanced (WHO DDE) preferred name and MedDRA will be used to code all medications.
- Study duration from day 1 (injection date) will be calculated as:

Study day in study = visit date – day 1 date + 1.

- For vital signs and laboratory summary tables, baseline is defined to be the last assessment prior to BOTOX injection.
- For by visit, vital signs and laboratory summary tables, there will also be a summary of the last post-baseline assessment.
- The algorithm presented in [Table 3](#), together with the rules below will be used to impute incomplete or missing dates for adverse events and medications as follows:
 - (a) AE start dates will be imputed as the minimum of the following:
 - initial imputed date, where target date = study drug injection date
 - complete end date
 - (b) Medication start dates will be imputed as the minimum of the following:
 - initial imputed date, where target date = study drug injection date – 1
 - complete end date
 - (c) AE and Medication end dates will be imputed as the minimum of the following:
 - initial imputed date, where target date = study exit date + 30
 - death date
 - Concomitant medication will be classified using the following convention: 1) If the start date of medication is after or on study drug injection date, then it will be counted as concomitant medication; 2) If the start date of medication is prior to the study drug injection date and stop date is on or after study drug injection date, then it will be counted as both prior medication and concomitant medication.

- All partial dates (including AE, concurrent and prior medication) will be listed “as is” in the data listings.

Table 3 **Initial Imputed Date Algorithm**

Available Year (YYYY)	Available Month (MM)			
	Missing	< Target Month	= Target Month	> Target Month
Missing	Target Date		—	
< Target Year	YYYY-12-31		YYYY-MM-LD	
= Target Year	Target Date	YYYY-MM-LD	Target Date	YYYY-MM-01
> Target Year	YYYY-01-01		YYYY-MM-01	

YYYY = available start date year; MM = available start date month; LD = last day of the month.

2.3.1 Diary Data Conventions

- For baseline and post-treatment visits, analyses will be based on the diary data collected over two consecutive days. “Wake time information” will be collected for each diary day including the time the patient woke up in the morning and presence/absence of night time leaking by accident (from the previous night), as well as the time and volume of urine collected on the first morning catheterization. “Day time information” will be collected for each diary day including date, time, and type of voiding episode [leak by accident (i.e. urinary incontinence), urinated with catheter, urinated without catheter (i.e. voluntary void)] for each daytime episode (from time after waking up to start the day and doing the first morning catheterization, and going to bed to sleep for the night). Lastly, “bed time information” will be collected for each diary day including the time the patient went to bed for the night.
- Note: Recording day time urinary events should begin *after* the 1st morning catheterization (as the urine expelled is from the previous night). In cases where the patient erroneously re-entered the first morning catheterization event as a day time event (ie, the time of 1st morning catheterization and the time of the first day time urinary event are the same), the event will not be included in the analysis for day time events.
- The visit windows [REDACTED] will be used to derive a patient’s diary parameters for each visit.
 - A valid diary day is defined as a day where there are one or more urinary episodes of any type (incontinence, catheterization, or voluntary void) during the daytime

collection period. In the case of patients who provide just one valid diary day within a visit window, the 2-day frequency of daytime urinary incontinence will be prorated with the value from the valid diary day.

- If there are no valid diary days within the window, the 2-day diary data will be set as missing for the visit.
- For baseline and post-treatment visits, the 2-day diary will be determined based on the following algorithm:
 - 1) Apply visit windows [REDACTED] which are based on days from the date of study drug injection.
 - 2) Determine the time of the first daytime urinary episode that is within the visit window (in the example below, 8:30 am on May 4). Count forward two consecutive daytime diary collection days. Note: the second daytime period should end within the window, i.e., prior to or on the last day specified in the window definition; otherwise, the nighttime or daytime data will not be used for the corresponding window. For baseline diary data, any urinary episodes collected up to the time of injection will be counted towards the baseline diary data.
 - 3) Using the example below, the first daytime period (used to determine normalized day time period) starts with a wake time of 7:30 am on May 4 and ends with a bedtime of 11:00 pm (going to bed to sleep for the night). The bedtime for May 4 starts at 11:00 pm and ends at the wake time of 12:00 pm on May 5. The second daytime period starts on 12:00 pm on May 5 (wake time) and ends at 1:00 am May 6. Note that the wake time and bedtime can go over 2 calendar days. In the data set, for a given daytime, even if the daytime period goes over 2 calendar dates it will be recorded under the same calendar date. The time of the day will be used to accurately attribute the date of the event.

Diary Day 1(May 3): Nighttime	Diary Day 1 (May 4): Daytime	Diary Day 2: (May 4): Nighttime	Diary Day 2 (May 5/6) : daytime
Nighttime leaked by accident:No	Wake time:7:30 am Morning catherization: 7:33 am Urinated (without using a catheter): 8:30 am Leaked by accident: 2:46 pm Urinated (using catheter): 2:46 pm Urinated (using catheter): 10:00 pm	Bedtime: 11:00 pm Nighttime leaked by accident: Yes	Wake time: 12:00 pm Morning catherization: 12:10 pm Urinated (without using a catheter): 2:30 pm Urinated (using catheter): 9:46 pm Leaked by accident: 12:05 am Bedtime: 1:00 am

- Missing daily average frequency of episodes of daytime urinary incontinence at baseline will be imputed using the median of all non-missing values at baseline within the same treatment group. For the primary analysis, for scheduled diary assessments up to the week 6 visit [REDACTED], the missing daily average frequency of episodes of daytime urinary incontinence will be replaced using the last observation carried forward (LOCF) approach. For scheduled diary assessments after the week 6 visit, no imputation method will be applied.
- The daily frequency of daytime urinary incontinence episodes will be normalized to a 12-hour daytime period. The following normalization algorithm will be used:
 - 1) Apply visit window [REDACTED] which uses days from treatment as reference.
 - 2) Identify wake time and bedtime within the visit window. Daytime period (in hours) is determined by time between wake time and bedtime for that day.
 - 3) Using the example below, 4 urinary incontinence episodes are recorded during the first daytime period of 16 hours (7:00am to 11:00pm), and 7 episodes recorded during the second daytime period of 14 hours (8:30am to 10:30pm).

April 3	April 4

Wake time 7:00am Bed time 11:00pm (16 hrs)
 
4 urinary incontinence episodes during the daytime collection period (beginning after the 1st morning catheterization and until bed time)
	
Wake time 8:30am Bed time 10:30pm (14 hrs)
 
7 urinary incontinence episodes during the daytime collection period (beginning after the 1st morning catheterization and until bed time)

On a given day, the number of daytime urinary incontinence episodes normalized to a 12-hour daytime period will be calculated by

$$\frac{12}{\text{daytime period}} \times \text{number of daytime urinary incontinence episodes} ,$$

which, in the example, adjusts to 3 ($= (12/16) \times 4$) and 6 ($= (12/14) \times 7$) normalized urinary incontinence episodes, respectively. The daily average frequency of daytime urinary incontinence episodes by the normalized daytime period in a given visit window will be 4.5 ($= (3 + 6)/2$) in this example.

- If wake time is missing, the missing wake time will be imputed by the first morning catheterization where urine volume is collected. If both the wake time and the first morning catheterization are missing then the morning wake time will be imputed by either the first urinary episode time of any type recorded on that day or 7:00 am, whichever comes earlier. If bedtime is missing, the missing time will be imputed by either the last urinary episode time of any type recorded on that day or 10:00 pm, whichever comes later.

3. Disposition and Exit Status

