## 5.4 Treatment Allocation Ratio and Stratification

Patients will be randomized centrally and assigned a randomization number prior to treatment. In addition, patients will be stratified by age (< 12 years or ≥ 12 years) and by the number of daytime urinary incontinence episodes reported at baseline (a total of ≤ 6 or > 6 episodes over the 2-day diary). One randomization number will be assigned to each patient prior to treatment and will be associated with 50, 100, or 200 U BOTOX in a 1:1:1 ratio.

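### SAP 2.3.1 counts injection-day diary entries towards baseline but normalizes them over a full waking day, so a baseline that includes the day of injection comes out too low

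*SAP*

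**What the plan says.** All the relevant rules are in SAP section 2.3.1.

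- **Choice of days.** The algorithm tells the programmer to "Determine the time of the first daytime urinary episode that is within the visit window" and then: "Count forward two consecutive daytime diary collection days". A guard follows: "the second daytime period should end within the window, i.e., prior to or on the last day specified in the window definition". The guard is in days, not clock time, and the windows themselves are redacted.
- **Baseline cut-off.** Directly after the guard, for baseline only, "any urinary episodes collected up to the time of injection will be counted towards the baseline diary data".
- **Valid day.** "A valid diary day is defined as a day where there are one or more urinary episodes of any type" in the daytime period. No minimum number of observed hours is set. One valid day in a window is enough to represent both.
- **Normalization.** The count is multiplied by 12 over the daytime period, and "Daytime period (in hours) is determined by time between wake time and bedtime for that day". A missing bedtime becomes the later of the last recorded episode and 10:00 pm. No rule ends the daytime period at injection.

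Elsewhere, SAP 5.1 takes baseline from the screening diary. Protocol 5.4 stratifies "by the number of daytime urinary incontinence episodes reported at baseline", using the 2-day total (at most 6, or more than 6). Protocol 8.2 has the diary checked for eligibility before study entry. SAP 2.1.1 uses actual strata in the analysis.

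**The concern.** The numerator and the denominator stop at different times. On an injection day the count stops at injection, while the hours run to bedtime, recorded or imputed. The hours after injection add nothing to the count but still dilute it.

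Baseline is part of the change score, is the covariate in the primary ANCOVA and may determine the stratum factor. It is also the reference for the responder variables in SAP 5.3 (reductions of at least 50%, 75% and 90%, and of 100%). The trial has no control treatment (Protocol 5.2), and its clinical hypothesis is a reduction from baseline (Protocol 2.2). The within-arm change therefore carries weight of its own, and that is the quantity a low baseline understates.

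**Working it through.** **1. The SAP's own example (SAP 2.3.1).** Four episodes in 16 hours and 7 in 14 hours: (12/16) × 4 = 3, (12/14) × 7 = 6, mean (3 + 6)/2 = 4.5. The stated 4.5 reproduces.

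**2. The same example with day 2 cut by injection.** Assumed: injection at 10:30 am, 2 hours after the 8:30 am wake time, and a constant leak rate of 7/14 = 0.5 per hour. That gives 1 episode before injection.

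- Recorded bedtime 10:30 pm: (12/14) × 1 = 0.86; baseline (3 + 0.86)/2 = 1.93.
- Bedtime missing, set to 10:00 pm (13.5 hours): (12/13.5) × 1 = 0.89; baseline (3 + 0.89)/2 = 1.94.
- Daytime period ended at injection (2 hours): (12/2) × 1 = 6; baseline (3 + 6)/2 = 4.5.

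Ending the denominator at injection restores the right value. The raw 2-day total falls from 4 + 7 = 11 to 4 + 1 = 5.

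**3. A typical child.** Assumed: 5 leaks per 15-hour day at a constant rate, day 1 complete, injection h hours after waking on day 2. A full day gives (12/15) × 5 = 4.0. The part-day gives (12/15) × (5/15) × h, and baseline is the mean of that and 4.0.

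| h | Part-day value | Baseline | Error | Raw 2-day total |
|---|---|---|---|---|
| 2 | 0.53 | 2.27 | -43% | 5.7 |
| 4 | 1.07 | 2.53 | -37% | 6.3 |
| 6 | 1.60 | 2.80 | -30% | 7.0 |

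The correct raw total is 10. Only the 2-hour case crosses the boundary at 6, and only if the actual stratum is rebuilt from this diary. If the injection day is the sole valid day, the part-day value is the whole baseline.

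**4. Responder status.** Suppose the 2-hour child has 1.5 episodes at week 6 (assumed). The true reduction is 1 - 1.5/4.0 = 62.5%. The computed reduction is 1 - 1.5/2.27 = 34%, so the child fails the 50% threshold.

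**5. Trial level.** Assumed: mean 4 per 12 hours, 15-hour days, 3 hours observed on the part-day. The part-day mean is 4 × 3/15 = 0.8, the baseline is (4 + 0.8)/2 = 2.4, and the shortfall is 1.6 per affected child. With a fraction f affected, the within-arm change shrinks by 1.6 × f. A simulation used 30 per group, 4,000 runs per setting, gamma-Poisson counts, week 6 rates at 0.60 and 0.35 of baseline, and ANCOVA on change with baseline as covariate. It gave:

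| Affected (assumed) | Dose difference | Its standard error | Within-arm change, better arm |
|---|---|---|---|
| 0% | -0.997 | 0.268 | -2.62 |
| 10% | -0.997 | 0.273 | -2.44 |
| 20% | -1.002 | 0.278 | -2.28 |
| 50% | -0.991 | 0.286 | -1.80 |

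The difference between doses does not move, its standard error rises slightly, and the within-arm change shrinks about as the formula predicts.

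**The case against.** The strongest reply is that the situation should hardly arise. Baseline comes from the screening diary, eligibility is confirmed from it, and the 2-day total is needed to stratify before randomization on day 1. If a complete 2-day diary lies earlier in the window, the first-episode rule selects it and keeps injection-day entries out. On this view the cut-off sentence only says that nothing after injection is baseline, and the redacted window may already end the day before.

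Most of this stands as an argument about frequency. The exposed case is a diary begun the day before injection or on the day itself, and that is an edge case. It does not remove the gap. If the window ended the day before, a cut-off at the time of injection would have nothing to act on. If the window includes that day, no visible rule matches the denominator to the shortened count.

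It is also fair to say that baseline has less leverage on the dose comparison than its several appearances suggest. With baseline as a covariate, ANCOVA on change and ANCOVA on the week 6 value give the same treatment contrast.

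A reader might infer three stronger points. The documents support none of them.

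- *Injection-day entries are added to a finished 2-day diary and the total is still divided by 2.* SAP 2.3.1 and 5.1 fix two consecutive days, normalized day by day, and no visible text adds a third.
- *An abandoned first screening diary would displace a later, complete one.* No visible text provides for repeat diaries, and the windows and the timing of the screening diary are redacted. The last-value baseline for vital signs and laboratory data (SAP 2.3) concerns other data and contradicts nothing here.
- *Post-treatment windows should use the days closest to the visit.* First in the window is a prespecified, deterministic rule. Preferring another is a matter of taste.

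**Conclusion.** The gap is real but narrow. As written, a baseline diary day that falls on the day of injection has a part-day count over a full-day denominator, and the resulting baseline is too low. Under the assumed 5 leaks per 15-hour day, the shortfall is 30% to 43% of the true value for injection 2 to 6 hours after waking on diary day 2. These are figures per child and rest on a constant leak rate. The documents do not give the number of affected children, which is probably small; the 0% to 50% range above is an assumption.

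A reader might infer that the primary comparison is biased. It should not be, because the error precedes blinded treatment. That conclusion assumes affected children are spread evenly over the analysed dose groups, and nothing in the documents ties diary timing to dose. What is affected is the within-arm change (understated), the percent-reduction responder rates (distorted) and precision (a small loss). No sample-size figure changes. The point is worth correcting because it sits in the derivation of the primary variable, but it does not threaten the dose comparison.

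**What to change.** Replace the baseline cut-off sentence in SAP 2.3.1 with:

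*Entries on the day of injection are not used for the baseline diary. Baseline uses two consecutive complete diary days (wake to bedtime) ending before the day of injection; if only one such day exists, the one-day rule applies. If no complete day exists before the day of injection, the daytime period on that day ends at the time of injection for the normalization.*

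The cost is SAP wording and a small programming change before database lock, with no new data. The downside is that a few patients may have a one-day baseline. In the last-resort case the estimate is noisy: with 2 observed hours each leak is multiplied by 12/2 = 6. Listing the patients whose baseline diary touches the day of injection would show how often the rule matters.
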